10.4.7 Safety Variables

Adverse events will be coded using the MedDRA dictionary. Frequencies and percentages of subjects with treatment-emergent adverse events (TEAEs), serious TEAEs, and TEAEs causing premature discontinuation will be provided by treatment group. An AE is treatment emergent if it 1) occurs after the first dose of randomized study treatment or 2) if it is present prior to receipt of randomized study treatment but worsens in severity or increases in frequency after the first dose of randomized study treatment. Furthermore, frequencies will be given of subjects with TEAEs by system organ class and preferred term; by system organ class, preferred term and maximal severity; by system organ class, preferred term for treatment-related AEs; by system organ class and preferred term for SAEs; and by system organ class, preferred term, and day of onset. Separate analyses will be performed for ocular specific and all AEs (including systemic).

Other safety endpoints including visual acuity, slit lamp biomicroscopy, dilated fundoscopy, and intraocular pressure, will be summarized by treatment group and visit using descriptive statistics. Changes or shifts from baseline will also be summarized where appropriate. For assessments performed by eye, study eye and fellow eye will be summarized separately. In addition, shifts from baseline to worst on-treatment value for ocular safety assessments will be summarized.

Immunogenicity will be summarized using discrete summary statistics. Counts and proportions will be presented by visit and treatment group. Exact 95% Clopper-Pearson confidence intervals will be presented. Treatment groups will be compared using Fisher's Exact Test, and exact 95% confidence intervals for the pairwise proportion differences will be constructed.

10.4.8 Interim Analyses

No interim analyses are planned for this study.

11 COMPLIANCE WITH GOOD CLINICAL PRACTICES, ETHICAL CONSIDERATIONS, AND ADMINISTRATIVE ISSUES

This study will be conducted in compliance with the protocol, current Good Clinical Practices (GCPs), including the International Conference on Harmonization (ICH) Guidelines, and in general, consistent with the Declaration of Helsinki. In addition, all applicable local, state, and federal requirements relevant to the use of investigational products in the countries involved will be adhered to.

11.1 PROTECTION OF HUMAN SUBJECTS

11.1.1 Subject Informed Consent

Informed consent must take place before any study specific procedures are initiated. Signed and dated written informed consent must be obtained from each subject and/or from the subject's parent or legal guardian prior to enrollment into the study. If the subject is under the legal age of consent, the consent form must be signed by a legal guardian or as required by state and/or local laws and regulations.

All informed consent/assent forms must be approved for use by the sponsor and receive approval/favorable opinion from an IRB/IEC prior to their use. If the consent form requires revision (eg, due to a protocol amendment or significant new safety information), it is the investigator's responsibility to ensure that the amended informed consent is reviewed and approved by Ora prior to submission to the governing IRB/IEC and that it is read, signed and dated by all subjects subsequently enrolled in the study as well as those currently enrolled in the study.

If informed consent is taken under special circumstances (oral informed consent), then the procedures to be followed must be determined by Ora and/or study sponsor and provided in writing by Ora and/or study sponsor prior to the consent process.

11.1.2 Institutional Review Board (IRB) Approval

This study is to be conducted in accordance with Institutional Review Board regulations (U.S. 21 CFR Part 56.103). The investigator must obtain appropriate IRB approval before initiating the study and re-approval at least annually.

Only an IRB/ERC approved version of the ICF will be used.

11.2 ETHICAL CONDUCT OF THE STUDY

This study will be conducted in accordance with the ethical principles that originated with the Declaration of Helsinki.

11.3 SUBJECT CONFIDENTIALITY

All personal study subject data collected and processed for the purposes of this study should be maintained by the investigator and his/her staff with adequate precautions as to ensure that the confidentiality of the data in accordance with local, state, and federal laws and regulations.

Monitors, auditors and other authorized representatives of Ora, the sponsor, the IRB/IEC approving this study, the Food and Drug Administration, the Department of Health and Human Services, other domestic government agencies, and other foreign regulatory agencies will be granted direct access to the study subject's original medical and study records for verification of the data and/or clinical trial procedures. Access to this information will be permitted to the aforementioned individuals to the extent permitted by law.

A report of the results of this study may be published or sent to the appropriate health authorities in any country in which the investigational product may ultimately be marketed, but the subject's identity will not be disclosed in these documents.

11.4 DOCUMENTATION

Source documents may include a subject's medical records, hospital charts, clinic charts, the investigator's study subject files, as well as the results of diagnostic tests such as X-rays, laboratory tests, and electrocardiograms. The investigator's copy of the eCRFs serves as the investigator's record of a subject's study-related data.

11.4.1 Retention of Documentation

All study related correspondence, subject records, ICFs, record of the distribution and use of all IPs and copies of eCRFs should be maintained on file for at least 2 years after the last approval of a marketing application in an ICH region and until there are no pending or contemplated marketing applications in an ICH region; or until at least 2 years have elapsed since the formal discontinuation of clinical development of the IP. These documents will be retained for a longer period if required by the applicable regulatory requirements or by an agreement with the sponsor. It is the responsibility of the sponsor to inform the investigator/institution as to when these documents no longer need to be retained.

If the responsible investigator retires, relocates, or for other reasons withdraws from the responsibility of keeping study records, custody must be transferred to a person who will accept the responsibility. The sponsor must be notified in writing of the name and address of the new custodian.

11.5 LABELING, PACKAGING, STORAGE, ACCOUNTABILITY, AND RETURN OR DISPOSAL OF INVESTIGATIONAL PRODUCT

11.5.1 Labeling/Packaging

Investigational drug will be packaged and labeled into clinical kits.

For the run-in period, 17 pouches will be packaged in a 2-week clinical kit. Each pouch will contain 2 single-use vials to provide a sufficient medication supply for one day.

For the treatment period, 17 pouches will be packaged in a 2-week clinical kit. Each patient will receive 4 kits. Each pouch will contain 2 vials to provide a sufficient supply of randomized study drug for one day.

11.5.2 Storage of Investigational Product

The study drugs must be stored in a secure area accessible only to the investigator and his/her designees. Study drug(s) must be refrigerated (2-8°C, Do Not Freeze), protected from light, and secured at the investigational site in a locked container.

11.5.3 Accountability of Investigational Product

The study drugs are to only be prescribed by the principal investigator or his/her named sub investigator(s), and is to only be used in accordance with this protocol. The study drugs must only be distributed to subjects properly qualified under this protocol to receive study drug. The investigator must keep an accurate accounting of the study drugs by maintaining a detailed inventory. This includes the amount of study drugs

received by the site, amount dispensed to subjects, amount returned to the site by the subjects, and the amount returned to the Sponsor upon the completion of the study.

11.5.4 Return or Disposal of Investigational Product

All IP will be returned to the sponsor or their designee or destroyed at the study site. The return or disposal of IP will be specified in writing.

11.6 RECORDING OF DATA ON SOURCE DOCUMENTS AND CASE REPORTS FORMS (CRFS)

All subject data will be captured in the subject source documents which will be transcribed in the eCRFs. The investigator is responsible for ensuring that study data are completely and accurately recorded on each subject's eCRF, source documents, and all study-related materials. All study data should also be attributable, legible, contemporaneous, and original. Recorded datum should only be corrected in a manner that does not obliterate, destroy, or render illegible the previous entry (e.g., by drawing a single line through the incorrect entry and writing the revision next to the corrected data). An individual who has corrected a data entry should make clear who made the correction and when, by adding to the correction his/her initials as well as the date of the correction.

Data entry of all enrolled and randomized subjects will use software that conforms to 21 CFR Part 11 requirements, and will be performed only by staff who have been trained on the system and have access to the system. Data will not be entered for screen failure subjects. An audit trail will be maintained within the electronic system to capture all changes made within the eCRF database. After the end of the study and database lock, compact discs (CDs) containing copies of all applicable subjects' eCRFs will be provided to each Investigator Site to be maintained on file by the Investigator.

11.7 HANDLING OF BIOLOGICAL SPECIMENS

Tear samples will be submitted to one or more central laboratories and / or analytical laboratories for processing, storage and analysis. All laboratories meet Good Laboratory Practice requirements.

11.8 PUBLICATIONS

Authorship and manuscript composition will reflect cooperation among all parties involved in the study. Authorship will be established before writing the manuscript. Ora and the study sponsor will have the final decision regarding the manuscript and publication.

13 APPENDICES

APPENDIX 1: SCHEDULE OF VISITS AND MEASUREMENTS

Procedure	Visit 1 Day -14±1		Visit 2 Day 1		Visit 3 Day 8±1	Visit 4 Day 15±2		Visit 5 Day 29±2		Visit 6 Day 57±3	
	Pre CAE®	Post CAE®	Pre CAE®	Post CAE®	Non CAE®	Pre CAE®	Post CAE®	Pre CAE®	Post CAE®	Pre CAE®	Post CAE®
Informed Consent / HIPAA	X										
Medical / Medication History and Demographics	X										
Medical / Medication Update			X		X	X		X		X	
Placebo Run-In Dispensation		X									
Placebo Run-in Collection			X								
Randomization				X							
Study Drug Dispensation				X	X ²		X		X		
Study Drug Instillation				X	X						
Study Drug Collection					X	X		X		X	
Diary Dispensation		X		X	X		X		X		
Diary Collection			X		X	X		X		X	
Review of Qualification Criteria	X	X	X	X							
Adverse Event Query	X	X	X	X	X	X	X	X	X	X	X
Pregnancy Test	X ¹									X ¹	
Drop Comfort Assessment				X							
Ora Calibra® Ocular Discomfort Scale	X	X	X	X	X	X	X	X	X	X	X
Ora Calibra® Ocular Discomfort & 4-Symptom Questionnaire	X	X	X	X	X	X	X	X	X	X	X
VAS Discomfort Scale	X	X	X	X	X	X	X	X	X	X	X
OSDI® Questionnaire	X		X		X	X		X		X	
Visual Acuity (ETDRS)	X		X		X	X		X		X	
Slit-lamp Biomicroscopy	X	X	X	X	X	X	X	X	X	X	X
Conjunctival Redness	X	X	X	X	X	X	X	X	X	X	X
Tear Collection			X							X	
Blood sampling for Immunogenicity testing				X			X		X		X
TFBUT	X	X	X	X	X	X	X	X	X	X	X
Fluorescein Staining	X	X	X	X	X	X	X	X	X	X	X
Lissamine Green Staining	X	X	X	X	X	X	X	X	X	X	X
CAE® Exposure	X		X		X		X		X		
Discomfort Grading during CAE® Exposure	X		X		X		X		X		
Schirmer's Test		X		X			X		X		X
Intraocular Pressure		X									X
Dilated Fundus Exam		X									X
Exit Subject from Study											X

¹To women of child-bearing potential, as defined. ²The Visit 2 study drug kit is redispensed at Visit 3.

APPENDIX 2: EXAMINATION PROCEDURES, TESTS, EQUIPMENT, AND TECHNIQUES

Visual Acuity Procedures (ETDRS Chart)

LogMAR visual acuity (VA) must be assessed using an Early Treatment Diabetic Retinopathy Study (ETDRS) chart. The procedure used will be consistent with the recommendations provided for using the ETDRS eye chart. VA should be evaluated at the beginning of each visit in the study (ie, prior to slit-lamp examination). VA testing should be done with most recent correction.

Equipment

The VA chart to be used is the ETDRS chart. If smaller reproduction (18" by 18", eg, from Prevent Blindness) wall charts are used, the subject viewing distance should be exactly 10 feet (or as specified by the manufacturer). In ALL cases, for purposes of standardizing the testing conditions during the study, all sites must use only the 'R' charts, and the right eye should be tested first. For reflectance (wall) charts, the chart should be placed frontally and well-illuminated.

Measurement Technique

The chart should be at a comfortable viewing angle. The right eye should be tested first. The subject should attempt to read each letter, line-by-line, left to right, beginning with line 1 at the top of the chart. The subject should be told that the chart has letters only, no numbers. If the subject reads a number, he or she should be reminded that the chart contains no numbers, and the examiner should then request a letter in lieu of the number. The subject should be asked to read slowly, so as to achieve the best identification of each letter. He/she is not to proceed to the next letter until he/she has given a definite response.

If the subject changes a response (eg, 'that was a "C" not an "O"') before he has read aloud the next letter, then the change must be accepted. If the subject changes a response having read the next letter, then the change is not to be accepted. The examiner should never point to the chart or to specific letters on the chart during the test.

A maximum effort should be made to identify each letter on the chart. When the subject says he or she cannot read a letter, he or she should be encouraged to guess. If the subject identifies a letter as 1 of 2 letters, he or she should be asked to choose 1 letter and, if necessary, to guess. When it becomes evident that no further meaningful readings can be made, despite encouragement to read or guess, the examiner should stop the test for that eye. However, all letters on the last line should be attempted as letter difficulties vary and the last may be the only one read correctly. The number of letters missed or read incorrectly should be noted.

LogMAR Visual Acuity Calculations

The last line in which a letter is read correctly will be taken as the base logMAR reading. To this value will be added the number "N x 0.02" where 'N' represents the total number of letters missed up to and included in the last line read. This total sum represents the logMAR VA for that eye.

For Example: Subject correctly reads 4 of 5 letters on the 0.2 line, and 2 of 5 letters on the 0.1 line.

Base logMAR	= 0.1
N (total number of letters incorrect on line 0.2 as well as 0.1)	= 4
N x T (T=0.02)	= 0.08
Base logMAR + (N x T)	= 0.1 + 0.08
logMAR VA	= 0.18

Repeat the procedure for the left eye.

In order to provide standardized and well-controlled assessments of VA during the study, all VA assessments at a single site must be consistently done using the same lighting conditions and same correction if possible during the entire study. If the same correction cannot be used (ie, a subject forgets his glasses), the reason for the change in correction should be documented.

Slit Lamp Biomicroscopy Procedures

Slit lamp biomicroscopic observations will be graded as Normal or Abnormal. Abnormal findings will be categorized as clinically significant (findings that may interfere with study parameters or otherwise confound the data as determined by the investigator) or not clinically significant (NCS). The following will be examined:

- Cornea
- Conjunctiva
- Anterior Chamber
- Iris
- Lens
- Eyelid

External magnification and biomicroscopy will be performed using a slit-lamp. Magnification will be consistent with standard clinical practice. The subject will be seated.

Dilated Fundoscopy

Dilated fundoscopy will be performed using indirect ophthalmoscopy. The investigator will make observations of the vitreous, retina, macula, choroid and optic nerve.

Observations will be graded as Normal or Abnormal. Abnormal findings that are clinically significant (as determined by the investigator that may interfere with study parameters or otherwise confound the data) and those that are not clinically significant will be described. A dilated fundoscopy examination should be performed if retinal disease is detected.

- Vitreous: Examination should emphasize the visual axis.
- Retina, Macula, Choroid: Include an observation of the retina and its blood vessels. Eyes should be excluded from the study if active inflammation is present.
- Optic Nerve: Significant damage or cupping to the optic nerve should be noted.

It is recommended that tropicamide 1% ophthalmic solution be used to dilate subjects. The use of cyclopentolate 1% ophthalmic solution is recommended as secondary dilating medication, should the need arise.

Intraocular Pressure

Intraocular pressure (IOP) will be measured in each eye by contact tonometry by the examiner and the results will be recorded in mmHg. A single measurement is made to obtain a determination of IOP. The same tonometer employing the Investigator's standard technique will be used throughout the study. In addition, all reasonable efforts will be made to have the same examiner obtain all IOP measurements for a given subject.

Tear Collection

Subjects will be seated at a reclined position. The investigator will collect tears for up to 5 min from each eye. The right eye will be collected, followed by the left eye. Once tears are collected, they will be pipetted into a separate tube for storage. Further details on tear collection process and storage will be found in a separate manual.

Blood Sampling for Immunogenicity Testing

Serum blood draws will be collected at Visits 2, 4, 5 and 6 for immunogenicity testing. Instructions for the collection, handling and shipping blood for immunogenicity testing are given in a separate laboratory manual.

Ora proprietary scales – Not for distribution without permission

Ora Calibra® Ocular Discomfort Scale for Dry Eye

Ora Calibra® Ocular Discomfort & 4-Symptom Questionnaire for Dry Eye

Visual Analogue Scale (VAS)

Subjects will be asked the following questions regarding ocular discomfort (unrelated to study drug instillation) at all visits.

The subject will be asked to rate each ocular symptom due to ocular dryness by placing a vertical mark on the horizontal line to indicate the level of discomfort. 0% corresponds to “no discomfort” and 100% corresponds to “maximal discomfort.”

Burning/ Stinging	0%	100%
		
Itching	0%	100%
		
Foreign Body Sensation	0%	100%
		
Blurred Vision	0%	100%
		
Eye Dryness	0%	100%
		
Photophobia	0%	100%
		
Pain	0%	100%
		

Ocular Surface and Disease Index (OSDI)[®] for Dry Eye

Ocular Surface Disease Index[®] (OSDI[®])²

Ask your patients the following 12 questions, and circle the number in the box that best represents each answer. Then, fill in boxes A, B, C, D, and E according to the instructions beside each.

Have you experienced any of the following during the last week?	All of the time	Most of the time	Half of the time	Some of the time	None of the time
1. Eyes that are sensitive to light? ...	4	3	2	1	0
2. Eyes that feel gritty?	4	3	2	1	0
3. Painful or sore eyes?	4	3	2	1	0
4. Blurred vision?	4	3	2	1	0
5. Poor vision?	4	3	2	1	0

Subtotal score for answers 1 to 5

(A)

Have problems with your eyes limited you in performing any of the following during the last week?	All of the time	Most of the time	Half of the time	Some of the time	None of the time	N/A
6. Reading?.....	4	3	2	1	0	N/A
7. Driving at night?	4	3	2	1	0	N/A
8. Working with a computer or bank machine (ATM)?.....	4	3	2	1	0	N/A
9. Watching TV?	4	3	2	1	0	N/A

Subtotal score for answers 6 to 9

(B)

Have your eyes felt uncomfortable in any of the following situations during the last week?	All of the time	Most of the time	Half of the time	Some of the time	None of the time	N/A
10. Windy conditions?.....	4	3	2	1	0	N/A
11. Places or areas with low humidity (very dry)?	4	3	2	1	0	N/A
12. Areas that are air conditioned?...	4	3	2	1	0	N/A

Subtotal score for answers 10 to 12

(C)

Add subtotals A, B, and C to obtain D
(D = sum of scores for all questions answered)

(D)

Total number of questions answered
(do not include questions answered N/A)

(E)

[figure not shown]
Please turn over the questionnaire to calculate the patient's final OSDI[®] score.

Evaluating the OSDI® Score¹

The OSDI® is assessed on a scale of 0 to 100, with higher scores representing greater disability. The index demonstrates sensitivity and specificity in distinguishing between normal subjects and patients with dry eye disease. The OSDI® is a valid and reliable instrument for measuring dry eye disease (normal, mild to moderate, and severe) and effect on vision-related function.

Assessing Your Patient's Dry Eye Disease^{1,2}

[figure not shown]
Use your answers D and E from side 1 to compare the sum of scores for all questions answered (D) and the number of questions answered (E) with the chart below.* Find where your patient's score would fall. Match the corresponding shade of red to the key below to determine whether your patient's score indicates normal, mild, moderate, or severe dry eye disease.

1. Data on file, Allergan, Inc.

Ora Calibra® Conjunctival Redness Scale for Dry Eye

Tear Film Break-Up Time (TFBUT)®

The examiner will instill [REDACTED] solution into the inferior conjunctival cul-de-sac of each eye. To thoroughly mix the fluorescein with the tear film, the subject will be instructed to blink several times. In order to achieve maximum fluorescence, the examiner should wait approximately 30 seconds after instillation before evaluating TFBUT.

With the aid of a slit-lamp, the examiner will monitor the integrity of the tear film, noting the time it takes to form micelles from the time that the eye is opened. TFBUT will be measured in seconds using a stopwatch and a digital image recording system for the right eye followed by the left eye. A Wratten #12 yellow filter will be used to enhance the ability to grade TFBUT.

For each eye, 2 measurements will be taken and averaged unless the 2 measurements are > 2 seconds apart and are each < 10 seconds, in which case, a third measurement would be taken and the 2 closest of the 3 would be averaged.

Fluorescein Staining

The examiner will instill [REDACTED] solution into the inferior conjunctival cul-de-sac of each eye. In order to achieve maximum fluorescence, the examiner should wait approximately 3-5 minutes after instillation before evaluating fluorescein staining. A Wratten #12 yellow filter will be used to enhance the ability to grade fluorescein staining. The staining will be graded with the Ora Calibra™ Corneal and Conjunctival Staining Scale.

Ora Calibra® Corneal and Conjunctival Staining Scale for Grading of Fluorescein Staining

[REDACTED]	[REDACTED]

Staining areas:

Lissamine Green Staining

The Investigator will instill [REDACTED] [REDACTED] into the inferior conjunctival cul-de-sac and wait approximately 30 seconds before evaluating staining. The subject will be instructed to blink several times to distribute the lissamine green. The staining will be graded with the Ora Calibra™ Corneal and Conjunctival Staining Scale.

Ora Calibra® Corneal and Conjunctival Staining Scale for Grading of Lissamine Green Staining

[REDACTED]	[REDACTED]

Staining areas:

Staining area for the Schirmer test strip

Unanesthetized Schirmer's Test

Schirmer's Tear Test will be performed according to the following procedure:

- Using a sterile Tear Flo Schirmer test strip (Rose Enterprises), a bend in the strip will be made in line with the notch in the strip
- The subject will be instructed to gaze up and in
- The Schirmer test strip will be placed in the lower temporal lid margin of each eye such that the strip fits tightly. Subjects will be instructed to close their eyes
- After 5 minutes have elapsed, the Schirmer strip will be removed. The length of the moistened area will be recorded (mm) for each eye

Drop Comfort Assessments

This procedure will be performed according to Ora, Inc. SOPs and/or guidance documents.

Subject-Reported Drop Comfort Scale

[figure not shown]
Ora Calibra® Drop Comfort Scale

Subject-Reported Drop Comfort Questionnaire

Ora Calibra® Drop Comfort Questionnaire

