8.8 STUDY DURATION

An individual subject's participation will involve 6 visits over approximately a 10-week (~70 days) period (56 days of treatment and 14 days pre-screening).

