### 15.2 Best-Corrected Visual Acuity (ETDRS)

The visual acuity procedure will be performed at each visit pre-CAE®. The logarithm of the minimum angle of resolution (logMAR) VA must be assessed using an ETDRS chart. The procedure used will

be consistent with the recommendations provided for using the ETDRS eye chart. Visual Acuity should be evaluated at the beginning of each visit in the study (i.e., prior to slit-lamp examination). Subjects should use their most recent correction to attain their best-corrected visual acuity (BCVA).

The observed and change from baseline visual acuity will be summarized for each eye (study eye and fellow eye) using continuous descriptive statistics by visit for each treatment group. A subject listing of visual acuity will also be produced.

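### Both eyes read from the 'R' chart alone at all six visits with no stated guard against recall, so a remembered letter can score as seen and a true acuity loss can be understated

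*Protocol*

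**What the plan says.** Protocol Appendix 2, Visual Acuity Procedures, sets one rule for every test: "all sites must use only the 'R' charts, and the right eye should be tested first". The reason given is "for purposes of standardizing the testing conditions during the study". After the right eye is scored, the instruction is "Repeat the procedure for the left eye", and no other chart is mentioned.

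On frequency, "VA should be evaluated at the beginning of each visit in the study". Protocol 8.8 states: "An individual subject's participation will involve 6 visits over approximately a 10-week (~70 days) period". The visit schedules in both the protocol and the SAP mark acuity at all six visits.

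On technique, letters are read line by line from left to right. "When the subject says he or she cannot read a letter, he or she should be encouraged to guess" All letters on the last line should be attempted. The score is the logMAR value of the last line with a correct letter, plus 0.02 for each letter missed up to and including that line.

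Best corrected acuity at all visits is a safety measure (Protocol 6.2, SAP 3.3). SAP 15.2 states: "The observed and change from baseline visual acuity will be summarized for each eye (study eye and fellow eye"), using descriptive statistics by visit and treatment group. Inclusion criterion 6 also sets an acuity threshold that each eye must meet at Visit 1.

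**The concern.** The procedure credits a correct letter however the subject produced it. If the letters never change, a subject who has lost resolution on a line can still supply letters remembered from an earlier visit. The left eye has a more recent source: the right eye read the same letters aloud minutes before. Because guesses are encouraged, a recalled letter is offered and scored.

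The error runs in an unhelpful direction for a safety measure, because it makes a real loss look smaller. Acuity has no test or decision threshold in the SAP, so readers will judge it by the raw size of the change. Protocol 1.2 describes one earlier human study, with two instillations in one day in the left eyes of healthy men. This trial doses both eyes twice daily for eight weeks.

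Eligibility is touched too: at Visit 1 the left eye is qualified on letters already read by the right eye.

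**Working it through.** **The protocol's own figure.** In the Appendix 2 example, 4 of 5 letters are read on the 0.2 line and 2 of 5 on the 0.1 line. Letters missed: 1 + 3 = 4. Score: 0.1 + 4 × 0.02 = 0.18. This matches the stated 0.18.

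**Value of one recalled letter.** An eye that reads all of the 0.2 line and nothing below scores 0.20. If it supplies one letter of the 0.1 line from memory, the base becomes 0.1 with four letters missed: 0.1 + 4 × 0.02 = 0.18. One recalled letter therefore improves the score by 0.02.

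**Prior readings of the chart.** Take 'R' as one letter set, read once per eye per visit. Before the test at visit v, the right eye has 2(v − 1) prior readings behind it and the left eye has 2(v − 1) + 1.

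| Visit | Before right eye | Before left eye |
|---|---|---|
| 1 | 0 | 1 |
| 2 (baseline) | 2 | 3 |
| 6 | 10 | 11 |

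From baseline to Visit 6 the count rises by 8 in each eye (10 − 2 and 11 − 3). The left eye differs in how recent its last exposure is, not in how fast exposure accumulates. For the smallest lines these counts are upper limits, because the test stops when no further useful reading is possible.

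**Effect on a true loss (assumed recall).** Let r be the share of letters no longer visible that the subject supplies from memory. Then recorded loss = true loss × (1 − r). The documents give no value for r, so the range below is illustrative.

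| True loss | r = 0 | 10% | 20% | 30% | 50% |
|---|---|---|---|---|---|
| 5 letters (0.10 logMAR) | 0.10 | 0.09 | 0.08 | 0.07 | 0.05 |
| 10 letters (0.20 logMAR) | 0.20 | 0.18 | 0.16 | 0.14 | 0.10 |

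**With one chart fixed for each eye.** Each chart is read once per visit, so prior readings before visit v are v − 1: 0 at Visit 1, 1 at Visit 2 and 5 at Visit 6, for either eye. No chart is read twice in one session.

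**The case against.** **'R' is not defined.** The appendix uses the plural, allows smaller reproductions and does not show the letters. It also asks for consistency with the recommendations for the ETDRS chart, which are not reproduced. This stands as a limit: one fixed letter set is an inference. It is a reasonable one, since the word 'only' and the standardization purpose both point to it, and a general reference does not displace an explicit restriction.

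**Standardization is a legitimate aim.** It is, but two charts assigned by eye, identical everywhere, are equally standardized.

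**The consequence is small.** This is correct. Acuity is a descriptive safety variable, reported beside adverse events, slit-lamp examination, fundoscopy and intraocular pressure.

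A reader might also infer four stronger claims, which the documents do not support:

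- *The left eye is always the worse affected.* SAP 15.2 reports change from baseline, and the left eye follows a same-session right-eye reading at baseline as well as at Visit 6. Dosing is bilateral. If both eyes lose acuity equally, the right eye cannot supply letters it no longer reads, and most of the left-eye excess goes. The tables are by study and fellow eye, so any order effect is also spread across both.
- *Scores drift toward improvement in a stable eye.* Letters below threshold were never reliably identified, and nothing has the examiner tell subjects whether an answer was right. There is little to remember unless the other eye sees better, and that advantage already exists at baseline.
- *A five-letter loss could vanish.* That result appears only if recall is assumed to supply all five letters.
- *Recall biases the comparison between arms.* The procedure is the same in every arm and creates no false difference. It can only shrink a real loss, and with it a real difference.

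**Conclusion.** The point holds as a directional risk, not a measured bias. As written, Appendix 2 has no guard against letter recall, either between eyes in one session or across visits. If 'R' is one letter set, a true acuity loss can be understated, most plausibly when it is confined to the left eye while the right eye still reads the letters. Left-eye acuity at Visit 1 can be overstated against inclusion criterion 6.

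Each recalled letter is worth 0.02 logMAR. How many letters are recalled is unknown, and the tabulated losses rest wholly on assumed recall shares. The co-primary endpoints, sample size, power and type I error are untouched. This is a minor improvement to a safety measurement, worth making because it is cheap.

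**What to change.** In Appendix 2, replace the 'R'-only rule with two letter charts: one fixed for the right eye and a different one fixed for the left, the same at all sites and visits. Record the chart used at each test.

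This removes same-session recall and reduces prior readings of each chart before Visit 6 from 10 and 11 to 5. It keeps each eye's baseline and follow-up on the same chart. Swapping charts between visits would also give 5 prior readings of each chart before Visit 6, but it would put some follow-up tests on a different chart from baseline.

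The cost is one extra chart at each of up to 3 sites and a short change to the text. Two downsides remain. The charts may differ slightly and constantly between right and left eyes; this cancels in change from baseline but not in observed values. Some recall across visits also persists. If the single chart is kept, the protocol should define 'R' and justify the choice, and acuity change should be listed by right and left eye.
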